Week 0	1	≤ 1
Week 4	29	[2, 57 ^a]

Rx Day calculated relative to the first dose date of study drug.

a. Before the first dose date of study drug on or after Week 16.

Table 18. Visit Windows for Summary of Study Drug Injections for Part A2

Window Label	Target Day	Interval
Week 16	1	≤ 1

Rx Day calculated relative to the Week 16 dose date.

Table 19. Visit Windows for Summary of Study Drug Injections for Part B

Window Label	Target Day	Interval
Week 28	1	≤ 1
Week 40	85	[2, 127]
Week 52	169	[128, 211]
Week 64	253	[212, 295]
Week 76	337	[296, 379]
Week 88	421	[380, 463 ^a]

Rx Day calculated relative to the first dose date of study drug in Part B.

a. Before retreatment.

Table 20. Visit Windows for Summary of Study Drug Injections for Subjects Retreated with Risankizumab for Relapse from Week 32 Through Week 70 (Inclusive)

Window Label	Target Day	Interval
Week 0	1	≤ 1
Week 4R	29	[2, 71]
Week 16R	113	[72, 155]

Rx Day calculated relative to the first dose date of retreatment.

Table 21. Visit Windows for Summary of Study Drug Injections for Subjects Retreated with Risankizumab for Relapse from Week 70 Through Week 82 (Inclusive)

Window Label	Target Day	Interval
Week 0	1	≤ 1
Week 4R	29	[2, 57]

Rx Day calculated relative to the first dose date of retreatment.

Table 22. Visit Windows for Summary of Study Drug Injections for Subjects Retreated with Risankizumab for Relapse After Week 82

Window Label	Target Day	Interval
Entry of retreatment	1	≤ 1

Rx Day calculated relative to the first dose date of retreatment.

Definition of Missing Data Imputation

No global imputation is taking place at the database level. Efficacy related imputations are outlined in Section 10.0. There is no imputation for missing values in the safety analyses.

Rounding of Numeric Results

Rounding will be performed for presentation of results. No rounding will be performed before or during analyses. The ROUND function of SAS will be used to round results.

When dichotomizing continuous variables, associated continuous variables will be rounded to 9 decimal points before applying the cutoff point to determine the response status (for example, percent change from baseline in PASI score will be rounded to 9 decimal places before comparing to 90%).

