The mean and median will be rounded for presentation to 1 decimal more than the data entered into the database. The standard deviation will be rounded to 2 decimal places more than the data entered into the database. The minimum and maximum values will be presented as entered into the database.

Probabilities will be rounded to 3 decimal places before assignment of statistical significance and will be presented in rounded format. Probabilities that round to zero or are reported by SAS as zero will be presented as "< 0.001." Probabilities that round to 1 or are reported by SAS as 1 will be presented as "> 0.999."

7.0 Demographics, Baseline Characteristics, Medical History, and Previous/Concomitant Medications

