10.0 Efficacy Analysis

10.1 General Considerations

The treatment effect will be evaluated based on a two-sided significance level of 0.05 (when rounded to three decimal places).

The Primary Analysis for Period B re-randomized subjects will be conducted after the last patient either has completed Week 52 visit or discontinues from the study, and at the time approximate to the database lock of all other global pivotal Phase 3 psoriasis studies, whichever occurs later. All endpoints will be analyzed up to Week 52, with the following exception:

- Categorical endpoints related to PASI and sPGA, using the LOCF method (defined in Section 10.1.4), will be analyzed up to the last visit that at least one subject has observed PASI and sPGA measurements, respectively.

To best maintain the study integrity for data beyond Week 52, blinded treatment assignments will not be disseminated to the sites, investigators, and patients until the end of study database lock.

Efficacy variables will be summarized in all efficacy populations. The efficacy analysis will be conducted in the ITT_A1 and the ITT_B_R populations. Only the primary and ranked secondary variables will be analyzed for the per-protocol populations using primary approach to handle missing data as described below.

Subjects' actual weight category and prior TNF antagonist exposure will be used as the strata in the stratified analyses.

10.1.1 **Analyses of Categorical Variables**

For categorical variables, frequencies and percentages will be summarized. Treatment comparison will be conducted using a Cochran-Mantel-Haenszel (CMH) test with stratification factors as strata for the analysis. The CMH test will use weights proposed by Greenland & Robins, which is calculated as follows:

$$\hat{\delta}_{MH} = \frac{\sum_{i=1}^u w_i \cdot \hat{\delta}_i}{\sum_{i=1}^u w_i}, \text{ where}$$

$\hat{\delta}_i = \frac{x_i}{n_i} - \frac{y_i}{m_i}$ denotes the risk difference in stratum $i, i = 1, \dots, u$

$w_i = \frac{n_i \cdot m_i}{n_i + m_i}$ denotes the weight of stratum $i, i = 1, \dots, u$

x_i denotes the number of patients with event in treatment₁ in stratum $i, i = 1, \dots, u$

y_i denotes the number of patients with event in treatment₂ in stratum $i, i = 1, \dots, u$

n_i denotes the number of patients on treatment₁ in stratum $i, i = 1, \dots, u$

m_i denotes the number of patients on treatment₂ in stratum $i, i = 1, \dots, u$

The estimated variance of $\hat{\delta}_{MH}$ is calculated as:

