10.2 Primary Efficacy Analysis

10.2.1 Primary Efficacy Analysis in Part A

There are two co-primary endpoints to assess the efficacy of risankizumab 150 mg for the treatment of moderate to severe plaque psoriasis in Part A. These are as follows:

- Achievement of $\geq 90\%$ reduction from baseline PASI score (PASI 90) at Week 16
- Achievement of an sPGA of clear or almost clear (0 or 1) at Week 16

The primary null hypotheses are that risankizumab 150 mg is not different from placebo in achieving PASI 90 and in achieving sPGA of clear or almost clear at Week 16.

The achievement of PASI 90 at Week 16 is the first co-primary endpoint. The difference in proportion of subjects achieving PASI 90 between treatment arms will be estimated and tested using the Cochran-Mantel-Haenszel risk difference estimate stratified by the stratification factors of baseline weight (≤ 100 kg vs. > 100 kg) and prior exposure to TNF antagonists (0 vs. ≥ 1).

The achievement of a sPGA of clear or almost clear at Week 16 is the second co-primary endpoint. The analysis method for the sPGA co-primary endpoint will be identical to that of the PASI 90 co-primary endpoint detailed above.

The co-primary endpoints of PASI 90 and sPGA clear or almost clear need to be significant simultaneously. Both endpoints will be tested using a two-sided test with a type I error rate of 0.05.

The primary analysis will be carried out in the ITT_A1 Population and the PP_A1 Population. Non-responder imputation will be used as the primary approach for missing values. LOCF and MI will be performed as sensitivity analyses.

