10.2.2 Primary Efficacy Analysis in Part B

Achievement of an sPGA of clear or almost clear (0 or 1) at Week 52 is the primary endpoint for Part B under re-randomization. This endpoint will be tested independently with a type I error rate of 0.05, for the ITT_B_R Population. A sensitivity analysis will also be performed on the same endpoint for the PP_B_R Population.

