10.4 Handling of Multiplicity

The statistical comparisons for the primary efficacy variable and the ranked secondary variables will be carried out in the hierarchical order. This means that statistically

significant results (P value ≤ 0.05) for the comparison in the higher rank (primary, then ranked secondary variables) are necessary to initiate the testing of the next comparison in the lower rank. Since a step-down procedure is used, each comparison will be tested at a significance level of 0.05 and overall alpha level of 0.05 will be preserved.

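### Rounding p-values to three decimals before judging significance lets any p below 0.0505 pass, so the nominal level is 5.05% rather than the stated 5% (minor)

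*SAP*

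**What the plan says.** Four parts of the SAP bear on the decision.

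- **Rounding convention, SAP 6.0 (Rounding of Numeric Results).** The subsection opens by tying rounding to presentation and adds: "No rounding will be performed before or during analyses". It names the SAS ROUND function. It then gives a nine-decimal rule for dichotomising continuous variables. For p-values it says: "Probabilities will be rounded to 3 decimal places before assignment of statistical significance".
- **Efficacy level, SAP 10.1.** "The treatment effect will be evaluated based on a two-sided significance level of 0.05 (when rounded to three decimal places".
- **Criterion, SAP 10.4.** Each step of the hierarchy requires "significant results (P value ≤ 0.05) for the comparison in the higher rank" before the next is tested, and the section concludes that "overall alpha level of 0.05 will be preserved".
- **Stated error rates.** For the co-primary endpoints, SAP 10.2.1 says: "Both endpoints will be tested using a two-sided test with a type I error rate of 0.05". For the Part B primary endpoint, SAP 10.2.2 says: "This endpoint will be tested independently with a type I error rate of 0.05". Protocol 7.2 also gives a two-sided type I error of 0.05. None of these three places mentions rounding, and SAP 14.1 does not list the rounding rule among the changes from the protocol.

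The 95% confidence interval in SAP 10.1.1 uses the 97.5% normal quantile, with the same estimate and variance as the p-value and no rounding.

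**The concern.** The criterion is inclusive, so rounding first can only turn a miss into a pass. A p-value just above 0.05 becomes 0.050 and qualifies, while no p-value at or below 0.05 is lost. The operating level is therefore not quite the level that the plan says it controls.

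Two consequences follow. First, both hierarchies are gated. If the Part B Week 52 test gave p = 0.0503, it would count as a success and open the Week 104 test, although the unrounded result missed 0.05. Second, the test and its interval could disagree, and the plan does not say which governs. Neither is likely. But a borderline result is the one case in which the exact rule gets argued over, and here the SAP supports both sides of that argument.

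**Working it through.** **Inputs.** Rounding to three decimals with SAS ROUND, where halves go up for positive values (SAP 6.0); criterion P ≤ 0.05 (SAP 10.4); CI quantile z0.975 (SAP 10.1.1); Part B planning rates of 90% and 75%, 1:2 allocation, 102 and 204 patients (protocol 7.7).

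**1. The plan's own figure.** With pooled variance and no continuity correction, the pooled rate is (0.90 × 102 + 0.75 × 204)/306 = 0.80. The active-arm size is

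n = [1.9600 × √(0.80 × 0.20 × 1.5) + 1.2816 × √(0.90 × 0.10 + 0.75 × 0.25/2)]² / 0.15²
= (0.9602 + 0.5494)² / 0.0225 = 101.3, so 102.

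This reproduces 102:204, and 306/0.8 = 382.5 gives 383. The sample size was therefore set at an unrounded two-sided 0.05.

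**2. Which p-values pass.**

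| Unrounded p | Rounded | ≤ 0.05? |
|---|---|---|
| 0.0500 | 0.050 | yes |
| 0.0504 | 0.050 | yes |
| 0.0504999 | 0.050 | yes |
| 0.0505 | 0.051 | no |

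The rule is equivalent to p < 0.0505.

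**3. Nominal level.** With p uniform under the null, P(p < 0.0505) = 0.0505. The excess is 0.0505 − 0.0500 = 0.0005, or 1% in relative terms. Critical |z| falls from 1.9600 (upper tail 0.025) to 1.9557 (upper tail 0.0505/2 = 0.02525). A simulation of 20 million null z statistics gave 0.04999 without rounding and 0.05049 with it. In a fixed-sequence hierarchy the bound on familywise error is the per-step level, so the bound within each hierarchy becomes 0.0505.

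**4. Test against interval.** For p = 0.0503, |z| = 1.9574. The CI limit nearer zero lies at (1.9574 − 1.9600) × SE = −0.0026 × SE in the direction of the effect, so the interval just includes zero although the test is called significant.

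**5. Effect on power at 102:204.** The null standard error is √(0.16 × (1/102 + 1/204)) = 0.04851. The alternative standard error is √(0.09/102 + 0.1875/204) = 0.04244.

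- Unrounded: (0.15 − 1.9600 × 0.04851)/0.04244 = 1.294, power 90.2%.
- Rounded: (0.15 − 1.9557 × 0.04851)/0.04244 = 1.299, power 90.3%.

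At 0.0505 the formula in step 1 would ask for 101 rather than 102 in the active arm. The plan used 0.05, so nothing in the sample size needs to change.

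**6. Chance of landing in the gap.** Exact binomial enumeration of the SAP's risk-difference statistic, simplified to one stratum, gives the probability that p falls between 0.0500 and 0.0505:

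- Part B, 102:204, 90% against 75%: about 2 × 10⁻⁹.
- Part B, 105:210, same rates: about 0.4%.
- Part A, 400:100, 65% or 80% against 5%: below 10⁻³⁷.
- Null case, 102:204, both rates 75%: about 0.0007.

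The Part B figures differ so widely because the statistic is discrete. Whether any attainable p-value sits in so narrow an interval depends on the exact group sizes.

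**The case against.** The strongest reply is that the rule is openly pre-specified. SAP 10.1 states the level together with its rounding convention, 6.0 gives the same convention, and it applies to every efficacy comparison. Nobody can choose it after seeing the data. This stands, and it is the main reason why the point is minor. It does not reconcile the rule with the claim in 10.4 that 0.05 is preserved, nor with the plain 0.05 in SAP 10.2 and protocol 7.2.

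A second reply is that the effect is negligible in practice. For the co-primary endpoints that is right. For Part B it is right at exactly 102:204, but that figure is fragile: 105:210 gives about 0.4%, and the number re-randomised depends on how many patients respond at Week 28. The normal approximation can also matter more than the rounding. In the same single-stratum enumeration the unrounded test has a size of about 7.1% at 400:100 with both rates 5%, and about 5.3% at 102:204 with both rates 75%. The fix therefore restores the nominal level; it does not make the true size exactly 5%.

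A reader might also infer that the rule flatly contradicts the SAP's own no-rounding sentence. The documents do not support that much. The subsection ties rounding to presentation without restricting it to presentation, and it goes on to give a specific rule for dichotomising. The p-value rule can be read as another explicit exception, applied after the test statistic has been computed. The two sentences sit awkwardly together, and the SAP does not reconcile them, but this is not a clear contradiction.

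**Conclusion.** The point holds as a minor one. As written, the decision rule is p < 0.0505. The nominal level is 5.05% per test and within each hierarchy, so the statement that 0.05 is preserved is untrue by 0.0005. A p-value between 0.0500 and 0.0505 would also put the test at odds with its 95% interval. This rests on the inclusive criterion in SAP 10.4, on ROUND taking 0.0505 up to 0.051, and on uniform null p-values. With discrete data the added error varies around 0.0005 and can be close to zero.

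Two further inferences should be resisted. It would be wrong to say that p = 0.0505 passes, because the bound is strict. It would also be wrong to extend the criticism to the three-digit rule for adverse-event p-values in SAP 11.1. That rule only decides which p-values are shown; it assigns no significance and belongs to no hierarchy, and protocol 7.3.4 plans no hypothesis tests for safety. Nothing here suggests a material threat to the co-primary conclusions or to the sample size.

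**What to change.** State in SAP 6.0 that the unrounded p-value is compared with 0.05 and that three decimals are used for display only. To do this, delete the clause in 6.0 that places rounding before the assignment of significance, and delete the parenthesis on rounding in 10.1. SAP 10.4 can then stand as written, and the test agrees with the interval in 10.1.1. Leave 11.1 unchanged.

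The cost is SAP wording only. No patients, data or visits are added, 102:204 stays as planned, and nominal Part B power is 90.2% rather than 90.3%. The change should be settled before unblinding, so that a borderline result cannot turn on which sentence is followed.

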7.1 Demographic and Baseline Characteristics

Demographics and Baseline characteristics will be summarized for each arm and for overall of the ITT populations. Continuous variables will be summarized with the number of non-missing observations by mean, standard deviation, first quartile, median,

third quartile, minimum and maximum values. Categorical data will be summarized using frequencies and percentages. Statistical tests will be performed to assess the comparability of the two arms at Randomization on ITT_A1 and at Re-Randomization on ITT_B_R. Per Protocol Populations will only be summarized in the accountability table. Treatment comparison will be made based on non-missing information. Continuous variables will be analyzed using one-way analysis of variance (ANOVA). Categorical variables will be analyzed using a two-sided Pearson's Chi-Square test (or an appropriate exact test if expected cell count < 5).

The following demographic and baseline parameters will be summarized.

Subject Demographics

- Sex (male, female)
- Age (years), defined as the number of years from date of birth to date of first drug
- Age categories (< 40 years, \geq 40 – < 65 years, \geq 65 years.)
- Race (American Indian or Alaska Native, Asian, Black or African American, Native Hawaiian or Other Pacific Islander, White, Multi Race)
- Ethnicity (Hispanic or Latino, Not Hispanic or Latino)
- Body weight (kg)
- Body weight category (\leq 100 kg, > 100 kg)
- Height (cm)
- BMI (kg/m^2)
- BMI category (< 25, \geq 25 – < 30, \geq 30)
- Prior exposure to TNF antagonists (0 versus \geq 1)

General Baseline Characteristics

- PASI (Psoriasis Area and Severity Index)
- BSA (Body Surface Area)
- sPGA categories

- NAPSI (Nail Psoriasis Severity Index)
- PSSI (Psoriasis Scalp Severity Index)
- PPASI (Palmoplantar Psoriasis Area Severity Index)
- Dermatology Life Quality Index (DLQI)
- HAQ-DI (HAQ Disability Index)
- Pain VAS (Visual Analog Scale)/Patient Global Assessment (PtGA) VAS (Visual Analog Scale)
- TJC/SJC (Tender/Swollen Joints)
- DAS28 (Disease Activity)

Psoriasis and Cardiovascular History

- Psoriatic arthritis (diagnosed, suspected, no)
- Cardiovascular Diseases (myocardial infarction, angina pectoris, transient ischemic attack, stroke, deep vein thrombosis)
- Cardiovascular Risk Factors (hypertension, hyperlipidemia, diabetes mellitus, obesity)

General Use

- Smoking status (Never-smoked, Ex-smoker, Currently smokes)
- Alcohol status (Non-drinker, drinks – no interference with participation in trial, drinks – possible interference with participation in clinical trial)

Prior Treatment

- Psoriasis Biologic Treatment History – by Response to Prior Treatment
- Psoriasis Treatment – by Therapy Type (topical therapy, phototherapy, photochemotherapy, non-biologic systemic therapy, TNF antagonist, other biologic)

Also, Physical Exam and Pregnancy Test will be presented in listing format.

7.2 Medical History

Medical history will be summarized using body systems and condition/diagnosis as captured on the eCRF. The body systems will be presented in alphabetical order and the conditions/diagnoses will be presented in alphabetical order within each body system. The number and percentage of subjects with a particular condition/diagnosis will be summarized for each treatment arm. Subjects reporting more than one condition/diagnosis within a body system will be counted only once for that body system.

7.3 Previous Treatment and Concomitant Medications

Prior and concomitant medications will be summarized by generic name. A prior medication is defined as any medication taken prior to the first dose of study drug. A concomitant medication is defined as any medication that started prior to the first dose of study drug and continued to be taken after the first dose of study drug or any medication that started after the first dose of study drug, but not after the last dose of study drug plus 21 days. The number and percentage of subjects who had taken medications will be summarized by generic drug name assigned by the World Health Organization (WHO) for both prior and concomitant medications.

7.4 Protocol Deviations

Number and percentage of subjects who reported at least one of the following protocol deviation categories will be provided.

- Subject entered into the study even though she/he did not satisfy entry criteria
- Subject who developed withdrawal criteria during the study and was not withdrawn
- Subject who received wrong treatment or incorrect dose
- Subject who received excluded or prohibited concomitant treatment

8.0 Patient Disposition

The number of subjects for each of the following categories will be summarized, for overall and for each treatment group in the ITT_A1 Population:

- Number of subjects randomized
- Number of subjects treated during Part A1
- Number of subjects who completed Part A1
- Number of subjects who discontinued study drug during Part A1
- Number of subjects who prematurely discontinued from Part A1

The number of subjects for each of the following categories will be summarized, for overall and for each treatment group in the ITT_B_R population:

- Number of subjects re-randomized
- Number of subjects treated at Part B
- Number of subjects who completed the Part B
- Number of subjects who received retreatment with risankizumab during Part B at different time points
- Number of subjects who discontinued study drug during Part B
- Number of subjects who prematurely discontinued from the Part B

In addition, the reasons for premature discontinuation will be summarized with frequencies and percentages.

Disposition tables will also be summarized in the ITT_A2, ITT_ARM2, and ITT_B_NR Populations.

In addition to patient disposition, number of screening failures and reasons for screening failure will also be summarized among all screened subjects in a subject screening status table.

9.0 Study Drug Exposure and Compliance

Summary of study drug exposure will be provided for each treatment arm for all ITT_A1, ITT_A2, ITT_ARM2, ITT_B_R, and ITT_B_NR populations, and the ALL_RZB population. Study drug compliance will be summarized in ITT_A1, ITT_A2, and ITT_B_R populations.

Study drug exposure (days) will be summarized using the sample size, mean, standard deviation, minimum, median and maximum for each treatment part. In addition cumulative exposure of RZB will be also summarized in the ALL_RZB Population. Study drug exposure will be summarized as follows:

Study Drug Exposure (in Days) in Each Period:

Part A1:

For subjects who did not continue into Part A2:

- Date of last injection in Part A1 – Date of first injection in Part A1 + 84.

For subjects who continued into Part A2: the minimum of

- Date of first injection in Part A2 – Date of first injection in Part A1.
- Date of last injection in Part A1 – Date of first injection in Part A1 + 84 days.

Part A2:

For subjects who did not continue into Part B:

- Date of last injection in Part A2 – Date of first injection in Part A2 + 84 days.

For subjects who continued into Part B: the minimum of

- Date of first injection in Part B – Date of first injection in Part A2.
- Date of last injection in Part A2 – Date of first injection in Part A2 + 84 days.

Part B:

For subjects who did not receive retreatment with risankizumab: the minimum of

- Date of last injection in Part B – Date of first injection in Part B + 84 days.
- Cutoff date of 01 September 2017 – Date of first injection in Part B (only for the primary analysis after the last patient either has completed Week 52 visit or discontinues from the study)

For subjects who received retreatment with risankizumab: the minimum of

- Date of first injection of retreatment – Date of first injection in Part B.
- Date of last injection in Part B – Date of first injection in Part B + 84 days.
- Cutoff date (01 September 2017) – Date of first injection in Part B (only for the primary analysis after the last patient either has completed Week 52 visit or discontinues from the study)

ALL_RZB:

For subjects who were re-randomized to placebo in Part B and received retreatment with risankizumab: the minimum of

- Date of last injection of risankizumab in Part A – Date of first injection of risankizumab + 84 days + Date of last retreatment of risankizumab – Date of first retreatment of risankizumab + 84 days.
- Date of last injection of risankizumab in Part A – Date of first injection of risankizumab + 84 days + Cutoff date for retreatment (22 September 2017) – Date of first retreatment of risankizumab (only for the primary analysis after the last patient either has completed Week 52 visit or discontinues from the study).

For all other subjects: the minimum of

- Date of last injection of risankizumab – Date of first injection of risankizumab + 84 days.

- Cutoff date (01 September 2017) – Date of first injection of risankizumab (only for the primary analysis after the last patient either has completed Week 52 visit or discontinues from the study)

Compliance

There will be a summary of the number of subjects receiving study drug and dose at each study drug administration visit. This will be repeated on the cumulative number of doses.

When computing compliance at each scheduled time point, the denominator for each week will include all subjects in each analysis population who have not prematurely discontinued study drug prior to the scheduled study drug injection. Subjects who have prematurely discontinued the study drug but have not prematurely discontinued the study are not used in the denominator.

